Planned Sample Size:	N= 150 total; 75 each arm			
Planned Study Duration:	3 years			
Major Inclusion Criteria:	
 
Trauma activation (Level I, II or III)
 
Age 18 years to 70 inclusive.
 
Blunt or penetrating injury
 
Need for pain treatment based upon an VNRS clinical pain measurement ≥ 50
 
Estimated time in Emergency Department > 30 minutes following informed consent
 
			
Major Exclusion Criteria:	
 
Advanced airway management prior to 1st dose administration
 
Known allergy to fentanyl, sufentanil, or meperidine
 
Known prisoner
 
Known pregnancy
 
ED pain treatment contraindicated per standard care
 
Estimated BMI >40
 
Significant respiratory depression
 
Known or suspected gastrointestinal obstruction, including paralytic ileus
 
			
Primary Outcome:	Verbally administered Numeric Rating Scale (VNRS) for clinical pain measurement (0-100) at 30 minutes following randomized medication administration			

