## I. Objective and Specific Aims

Our objective is to perform a prospective, randomized, interventional trial of Emergency Department (ED) administration of DSUVIA versus standard care pain management comparing pain treatment outcomes in injured patients with moderate to severe pain.

**AIM #1:** To determine if, among injured patients with moderate to severe pain, treatment with DSUVIA compared to standard care pain treatment in the ED reduces the Verbally administered Numeric Rating Scale (VNRS) for clinical pain measurement (0-100) at 30 minutes.

Hypothesis #1: Null Hypothesis: There will be no difference in the pain score at 30 minutes of patients who received DSUVIA as compared to standard care pain medicine in trauma patients

**AIM #2**: To determine if, among injured patients with moderate to severe pain, treatment with DSUVIA compared to standard care pain treatment in the ED reduces adverse effects and events related to pain medication(s) including nausea/vomiting, headache, dizziness, hypoxia, hypotension, and need for advanced airway.

Hypothesis #2: Null Hypothesis: There will be no difference in the rate of adverse events of nausea/vomiting, headache, dizziness, hypoxia, hypotension and need for advanced airway in patients who received DSUVIA as compared to standard care pain medicine in trauma patients.

**AIM #3:** To determine if, among injured patients with moderate to severe pain, treatment with DSUVIA compared to standard care pain treatment in the ED improves pain treatment effectiveness including serial VNRS scores (every 30 minutes), the need for rescue narcotic administration, the time needed to reduce the VNRS pain score by 10 points, time-weighted summed pain intensity difference, patient global assessment (PGA), Six Item Screener (SIS) cognitive assessment and Richmond Agitation-Sedation Scale scores.

Hypothesis #3: Null Hypothesis: There will be no difference in the pain treatment effectiveness, need for rescue narcotic administration, time to reduction of 10 points of VNRS pain score by 10 points, the time-weighted summed pain intensity difference, patient global assessment, Six-Item Screener and the Richmond Agitation-Sedation Scale scores in patients who received DSUVIA as compared to standard care pain medicine in trauma patients.

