The NAEMSP guidelines focus on intravenous (IV) fentanyl and morphine because of wide availability among American EMS services. Use of IV opioids is limited by the need to obtain IV access, which can be time consuming, is associated with a significant failure rate, and may lead to increased exposure in a tactical environment. The US military uses oral transmucosal fentanyl citrate (OTFC) which can be administered without IV access, but has slow absorption. Furthermore, safety data on OTFC, outside of long-term analgesia for cancer patients, is not well described. Given these significant limitations, an alternative to IV opioid analgesics in necessary. The ideal agent has robust stability, easy delivery, rapid onset, minimizes altered mental status and has a wide therapeutic index. In addition, the ideal agent would have a longer duration of action and an improved side effect profile as compared to the current standard care.

Sufentanil is a potent opioid analgesic derived from fentanyl with no active metabolites, rapid onset, and a therapeutic index superior to morphine and fentanyl. Sufentanil is highly lipophilic and rapidly achieves equilibrium in the brain; the time to analgesia is similar to IV morphine. When administered sublingually, sufentanil is 53% of the IV bioavailability within one minute and provides analgesia within 15 minutes. Sufentanil has a low incidence of side effects, with nausea, headache, dizziness, and vomiting being the most common. As with any opioid, respiratory depression and hypoxia can occur but was observed to be <1%. Similar studies found no clinically significant changes in vital signs after the administration of sublingual sufentanil in post-operative patients. Sufentanil was effective in a cohort of patients with painful injuries presenting to the ED with pain reduction seen in less than 15 minutes and persisting for 2 hours.

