These data suggest that in this cohort of injured patients with moderate to severe pain, sublingual sufentanil (DSUVIA) may provide similar analgesia to IV opioids. Similar to standard care with IV fentanyl or morphine, sufentanil (DSUVIA) is effective, rapid in onset, and has a favorable side effect profile. DSUVIA has the advantage of sublingual administration, precluding the need for IV access while providing rapid analgesia. In addition, sublingual administration of sufentanil provides longer duration of analgesia compared to IV fentanyl and more rapid absorption and analgesia then OTFC. The current management of pain in this injured cohort is inadequate and demonstrates the need to determine the efficacy and safety of DSUVIA (sublingual sufentanil) as compared to standard care for pain management in the prehospital setting.

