#### Secondary Outcome Definitions:

**Hypoxia, hypotension or need for advanced airway:** The principal safety outcome for the trial will be the incidence of serious adverse events following the first dose of analgesic following randomization including hypoxia (SpO2 < 90%), hypotension (SBP < 90 mmHg) or the need for advanced airway management (placement of an endotracheal tube, supraglottic airway or bag mask ventilation) until ED discharge (up to 120 minutes), when feasible.

Composite outcome of nausea, vomiting, headache, and/or dizziness requiring treatment: The incidence of nausea, vomiting, headache, and/or dizziness requiring treatment will be recorded for initial 30 minutes, when feasible.

Verbally administered Numeric Rating Scale (VNRS) pain measurements (0-100) at 30- minute intervals: VNRS for clinical pain (0-100) measurements at approximate 30-minute intervals until discharge from the ED (up to 120 minutes) or rescue narcotic administration, will be obtained when feasible.

**Patient Global Assessment (PGA) of Pain Control at 30-minute intervals:** The PGA of the method of pain control at approximate 30-minute intervals until discharge from the ED (up to 120 minutes) or rescue narcotic administration, will be obtained when feasible. The research team will read the following statement aloud to the subject and the response will be recorded: "Overall, would you rate this method of pain control during the last 30 minutes/hours as being poor (1), fair (2), good (3), or excellent (4)?"

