## VI. Statistical Analysis Plan

Random Assignment: Participants will be randomly assigned in a 1:1 ratio to either DSUVIA or standard of care, stratified by site. Within each stratum, random assignment will be blocked, with random block size of two and four.

Analyses: All analyses will be carried out based on the intention-to-treat principle. Of those randomly assigned, the analyses will begin by describing the overall characteristics of the study population at the time of random assignment. Baseline characteristics will be described overall using summary statistics (e.g., means, standard deviation, percentages) and graphical techniques (e.g., histograms, box plots). Baseline characteristics between the two groups will be compared using t-tests or Wilcoxon tests for continuous variables and a chi-square tests for discrete variables.

The analyses for each aim are presented below.

AIM #1: To determine if, among injured patients with moderate to severe pain, treatment with DSUVIA compared to standard care pain treatment in the ED reduces the Verbally Administered Numeric Rating Scale (VNRS) for clinical pain measurement (0-100) at 30 minutes.

A t-test will be used to compare the mean VNRS scores between the two treatment groups. A multivariable regression model will be used to compare the means after adjusting for stratification

variables (i.e., site) and baseline characteristics not balanced through random assignment. All assumptions of the analyses will be tested (e.g., normality of residuals). If any assumptions are violated, transformations of the data will be investigated and the transformed data will be analyzed and evaluated. If an adequate transformation cannot be identified, nonparametric methods will be used.

AIM #2: To determine if, among injured patients with moderate to severe pain, treatment with DSUVIA compared to standard care pain treatment in the ED reduces adverse effects and events related to pain medication(s) including nausea/vomiting, headache, dizziness, hypoxia, hypotension, and need for advanced airway.

The adverse events will be analyzed in composite (any of them) and individually. For each, a chi-square test will be to compare the proportion of events between the two treatment groups. A multivariable logistic regression model will be used to compare the proportions after adjusting for stratification variables (i.e., site) and baseline characteristics not balanced through random assignment

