# AIM #4: To determine if, among injured patients with moderate to severe pain, treatment with DSUVIA compared to standard care pain treatment in the ED improves Healthcare Professional Global Assessment (HPGA) of the Method of Pain Control and health care provider survey scores.

Scores to the HPGA will be based on a four-point scale. A 2x4 chi-square test will be used to compare the distribution of scores across the two treatment groups. An ordinal polytomous logistic regression model will be used to compare the distribution of proportions after controlling for stratification (sites) and baseline characteristics not balanced through random assignment. The same analysis will be repeated on the health care provider survey scores, with the modification to account for a five-level outcome.

**Sample Size**: The sample size calculations are based on the analyses of the primary aim (Aim 1) of the study. To detect a minimum effect size of 0.45, a sample size of 150 subject is needed (75 per group), assuming a type I error of 0.05, a two-sided alternative hypothesis, and 80% power. Thus, assuming a standard deviation of 21 (Karcioglu, 2003), a difference of 7.1 can be detected between the mean VNRS scores.

**Missing data**: Every attempt will be made to minimize the amount of missing data. Give the short timewindow to collect data, missing data should be minimal. However, in the event that there is missing data for the outcomes, the pattern of missingness will be evaluated. Assuming that the data will be missing at random, multiple imputation techniques will be used to impute data and carry out the proposed analyses.

**Subgroup**: Analyses will be carried out for pre-defined subgroups, specifically: sex (male/female), Injury Severity Score (ISS < or  $\ge 16$ ), age (< or  $\ge 50$ ), blunt versus penetrating injury, history of prior opioid use (Y/N), air versus ground prehospital transport, transport origin (scene versus outside ED). For all subgroup analyses, regression models will be used to assess if there is a differential treatment effect by subgroup. Regression models will include main effects for treatment and the indicator of the subgroup, as well as the two-way interaction between treatment and the subgroup indicator. A statistically significant interaction will indicate a differential treatment effect.

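### Aim 2's final safety comparison rests on chi-square and logistic tests with 75 per arm, which say almost nothing about events near 1%; report risk differences with score-based intervals instead

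*Combined protocol and SAP*

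**What the plan says.** The Protocol Synopsis lists safety beside effectiveness and acceptability as something the trial will examine against standard care. Hypothesis #2 in section I gives the null: "There will be no difference in the rate of adverse events of nausea/vomiting, headache, dizziness, hypoxia, hypotension and need for advanced airway". Under Secondary Outcome Definitions, "The principal safety outcome for the trial will be the incidence of serious adverse events following the first dose of analgesic", made up of hypoxia, hypotension or advanced airway management until ED discharge (up to 120 minutes). Nausea, vomiting, headache or dizziness requiring treatment form a separate composite.

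Section VI, Analyses, Aim #2, analyses the events as one any-event composite and singly. For each, "a chi-square test will be to compare the proportion of events between the two treatment groups", and a logistic model then adjusts for site and for baseline characteristics that turn out unbalanced. The plan names no risk difference, no confidence interval and no method for sparse tables. It does not say how a non-significant safety result is to be read.

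On size, the Synopsis gives "N= 150 total; 75 each arm", and section VI says "The sample size calculations are based on the analyses of the primary aim (Aim 1) of the study". Section II supplies the only event rate: with sufentanil, "respiratory depression and hypoxia can occur but was observed to be <1" percent. Section X expects relatively few serious adverse events.

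**The concern.** Safety is a named aim with its own principal outcome, but the analysis commits only to a significance test and an odds-ratio model. With few events, a non-significant result is likely whether or not DSUVIA carries an excess, so the p-value hardly distinguishes the two. The reader of the final report needs to know how large an excess the data still allow, and nothing in the plan produces that figure. The same data could supply it. The hypoxia, hypotension or airway outcome is also not listed for analysis as a composite in its own right; Aim #2 names only the any-event composite and the single events.

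**Working it through.** **Inputs.** 75 per arm (Synopsis). Two-sided 0.05: section VI states this for the sample size, "assuming a type I error of 0.05, a two-sided alternative hypothesis, and 80% power", and I assume it carries over to Aim 2. Control-arm rates: 1%, taken from the section II figure of below 1% for sufentanil; 5% and 10% are assumptions, because the documents give no rate for hypotension, for the control arm or for any composite.

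**The plan's own figure.** For a standardised effect of 0.45, n per arm = 2(1.960 + 0.842)²/0.45² = 77.5, so 78; power at 75 per arm is 0.787. That is close to the stated 75 and 80%, but it concerns pain score. No corresponding figure exists for Aim 2.

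**Power of the planned test.** Sum the product of two binomials (n = 75 each) over all tables whose uncorrected Pearson chi-square exceeds 3.841. Fisher's exact test is shown for comparison.

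| Control | DSUVIA | Chi-square power | Excess missed | Fisher power |
|---|---|---|---|---|
| 1% | 2% | 0.032 | 97% | 0.002 |
| 1% | 3% | 0.092 | 91% | 0.013 |
| 1% | 5% | 0.278 | 72% | 0.094 |
| 5% | 10% | 0.218 | 78% | 0.128 |
| 5% | 15% | 0.554 | 45% | 0.445 |
| 5% | 20% | 0.827 | 17% | 0.760 |
| 10% | 20% | 0.410 | 59% | 0.323 |
| 10% | 30% | 0.885 | 12% | 0.837 |

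The DSUVIA rate at which chi-square power reaches 80% is about 10.9% against 1%, 19.4% against 5% and 27.4% against 10%. Moving to Fisher's test would deal with the approximation but lower the power further.

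**Sparse tables at 1%.** Expected events per arm = 75 × 0.01 = 0.75, too few for the chi-square approximation. P(no event in one arm) = 0.99^75 = 0.471. P(at least one arm empty) = 1 − (1 − 0.471)² = 0.72. P(both empty) = 0.471² = 0.22. When one arm is empty the maximum-likelihood odds ratio has no finite estimate; when both are empty the model cannot be fitted at all.

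**One table worked through.** With 6/75 on DSUVIA and 1/75 on control, chi-square = 150 × (6×74 − 1×69)² / (75 × 75 × 7 × 143) = 3.75, p = 0.053. The Wilson limits are 3.7% to 16.4% and 0.2% to 7.2%. The Newcombe 95% interval around the difference of 6.7 points runs from −0.6 to +15.1 points. The test gives one non-significant p-value; the interval shows that an excess of 15 points is not excluded.

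**What the interval gives in sparse data.** Newcombe 95% limits in points, DSUVIA against control: 0 vs 0, −4.9 to +4.9; 1 vs 1, −5.9 to +5.9; 3 vs 1, −3.7 to +9.9; 4 vs 4, −8.3 to +8.3. It remains defined where the odds ratio is not.

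**The case against.** Four things can be said for the plan.

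First, a reader might infer that safety is judged only by these tests. The documents do not support that. Section VI, Interim Analyses, has the DSMB review adverse events and weigh safety outcomes by treatment group, and section X has sites assess relatedness and events reviewed for changes in nature, severity or frequency. This stands. Those reviews guide trial conduct, however, and do not produce the final comparative result.

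Second, a reader might infer that a non-significant test will be presented as proof of equal safety. No section says so. Hypothesis #2 is a null hypothesis in the same form as those for the other aims, and Aim 2 asks whether DSUVIA reduces adverse events, so strictly a non-significant result is a failure to show a reduction. This too stands; the defect is that the plan neither guards against the misreading nor supplies a more informative result.

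Third, it is tempting to say that any several-fold excess of hypoxia or hypotension will almost certainly go unseen. That fails at higher rates: a fourfold excess from 5% is detected 83% of the time and a threefold excess from 10% about 89%. No hypotension rate is given, and the any-event composite includes the side effects that section II calls most common. The 6 against 1 example is also one event short of significance: 7 against 1 gives chi-square = 150 × 450² / (75 × 75 × 8 × 142) = 4.75.

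Fourth, the plan names no interval for any aim, section IV calls this a pilot, and a logistic model ordinarily comes with an interval. For commoner events that last point has force. For events near 1% it does not, because the odds ratio often does not exist.

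**Conclusion.** The point holds for the final between-arm analysis of Aim 2. For events near the one rate that the documents give, the planned methods are nearly uninformative: a threefold excess from 1% is missed about 91% of the time and a fivefold excess about 72%, and there is a 72% chance that at least one arm has no events. For events at 5% to 10%, a doubling is missed 78% to 59% of the time, while larger multiples are reasonably detectable.

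These figures assume 75 analysed per arm, two-sided 0.05 for Aim 2, and a control rate equal to the upper end of the sufentanil figure. The 5% and 10% rates are assumptions. The primary aim is not affected. The documents make no claim of comparable safety, so the plan does not need a non-inferiority margin. It needs a method that still reports something useful when events are few.

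**What to change.** In section VI, Analyses, Aim #2:

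- Make the main result the event counts by arm and the risk difference (DSUVIA minus standard care) with a two-sided 95% Newcombe or other score-based interval.
- Report it for the hypoxia, hypotension or airway outcome, the nausea, vomiting, headache or dizziness composite, the any-event composite, and each event singly.
- Keep the chi-square p-value as supportive.
- Add a sentence such as: *A non-significant test will not be reported as absence of a difference in adverse events; the safety conclusion will state the upper 95% limit for the excess risk on DSUVIA.*

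The cost is SAP wording and one more column in the safety tables, with no added patients or data. The downside is a weaker-looking safety statement: the limits will be wide, with an upper limit of about 5 points even if neither arm has an event.

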# AIM #4: To determine if, among injured patients with moderate to severe pain, treatment with DSUVIA compared to standard care pain treatment in the ED improves Healthcare Professional Global Assessment (HPGA) of the Method of Pain Control and health care provider survey scores.

Scores to the HPGA will be based on a four-point scale. A 2x4 chi-square test will be used to compare the distribution of scores across the two treatment groups. An ordinal polytomous logistic regression model will be used to compare the distribution of proportions after controlling for stratification (sites) and baseline characteristics not balanced through random assignment. The same analysis will be repeated on the health care provider survey scores, with the modification to account for a five-level outcome.

**Sample Size**: The sample size calculations are based on the analyses of the primary aim (Aim 1) of the study. To detect a minimum effect size of 0.45, a sample size of 150 subject is needed (75 per group), assuming a type I error of 0.05, a two-sided alternative hypothesis, and 80% power. Thus, assuming a standard deviation of 21 (Karcioglu, 2003), a difference of 7.1 can be detected between the mean VNRS scores.

**Missing data**: Every attempt will be made to minimize the amount of missing data. Give the short timewindow to collect data, missing data should be minimal. However, in the event that there is missing data for the outcomes, the pattern of missingness will be evaluated. Assuming that the data will be missing at random, multiple imputation techniques will be used to impute data and carry out the proposed analyses.

**Subgroup**: Analyses will be carried out for pre-defined subgroups, specifically: sex (male/female), Injury Severity Score (ISS < or  $\ge 16$ ), age (< or  $\ge 50$ ), blunt versus penetrating injury, history of prior opioid use (Y/N), air versus ground prehospital transport, transport origin (scene versus outside ED). For all subgroup analyses, regression models will be used to assess if there is a differential treatment effect by subgroup. Regression models will include main effects for treatment and the indicator of the subgroup, as well as the two-way interaction between treatment and the subgroup indicator. A statistically significant interaction will indicate a differential treatment effect.

Randomization of Ineligible Subjects: It is anticipated that there will be a small proportion of patients enrolled who receive DSUVIA or standard care that in retrospect will not have met the entry criteria and are thus ineligible. In this circumstance, patients will be analyzed according to the group to which they were randomized. Subgroup analyses based on eligibility criteria will be performed if the number of patients so affected is large. However, based on the relatively limited inclusion and exclusion criteria it is anticipated that the frequency of this event will be low.

Non-adherence: In some circumstances, patients may receive standard care instead of the DSUVIA intervention when randomized to DSUVIA. Non-adherence is most likely to occur in the case of the patient who requires intervention and despite DSUVIA being available, is unable to be provided. In the event of inappropriate handling or unsuccessful administration of the DSUVIA, a second dose of DSUVIA may not be administered. Once a physician has assessed the subject, if appropriate, the subject may receive a dose of standard care pain medication and continue in the DEEP study. Fortunately, this event is relatively rare. In keeping with the intention-to-treat analytic design, these patients will be analyzed with the group to which they were randomized.

Interim Analyses: Throughout the course of the study, the DSMB will review recruitment, retention, adherence to assigned intervention, data completeness, protocol deviations, and adverse events. Safety data will be examined on an ad hoc basis in the event that unexpected safety concerns arise from study data or from external research or literature.

The DSMB will review the primary and secondary outcomes bi-annually. Prior to initiation of the trial, the final monitoring plan will be developed to serve as the guide to the DSMB's decision-making process concerning early stopping of the trial. The interim analysis will consist of two components, efficacy evaluation and futility evaluation. The purpose of the efficacy evaluation is to detect early sign of treatment effect early in the study. The purpose of the futility analysis is to assess if the study is unlikely to achieve a statistically significant effect. In making the decision to recommend termination of the study, the DSMB shall be guided by several types of information: (i) a formal stopping rule based on the primary analysis (comparison of treatment groups on the primary outcome), (ii) information on safety outcomes by treatment group, (iii) consistency between results for primary and secondary outcomes, (iv) consistency of treatment effects across subgroups, and (v) conditional power.

We have designed this trial with one-interim analyses before the final analysis. The number of interim analyses will be finalized in discussion with the DSMB prior to the initiation of the study. The interim analysis plan is based on the Lan and Demets approach utilizing an O'Brien-Fleming spending function to

determine alpha spending and test boundaries. A formal interim analysis of efficacy will be performed when 50% of the randomly assigned participants have completed the assessment of the primary outcome. We will use a t-test to test for difference. The level of significance will maintain an overall p-value of 0.05 according to O'Brien-Fleming stopping boundaries leaving a p value of 0.003 and 0.049 for the interim and final analyses, respectively. This translates to a two-sided z-value for the interim and final analyses of +/-2.96 and +/-1.97, respectively.

In addition, the futility of the study will be evaluated at the time an interim efficacy test is conducted. Specifically, the conditional power will be calculated. If the condition power is less than value prespecified by the DSMB (e.g., <20%), we can conclude that it would be futile to continue with the investigation.

Surveillance for Outcomes and Data Elements: Data will be collected prospectively as patient care progresses. This will include a review of the prehospital patient care report(s), ED and electronic/ paper hospital records.

In-Hospital Resuscitation Elements: Demographics, prehospital assessments and narcotic treatments, injury mechanism and characteristics, ED vitals, ED procedures/interventions, injury severity, injury severity scoring and assessment, ICU days and length of stay.

Data Entry: The DCC will create web-based HTML forms to collect necessary information from all participating sites. Web entry forms will have dynamic features such as edit and data type checks. Details and clarification about data items will be provided using pop-up windows. Data encryption and authentication methods will be used. Additional features will be built into the web entry forms including: forms transmission history, access to past forms, tracking of data corrections, and the capability to save and re-load incomplete forms. The subjects will be identified by a study number only. All clinical interventions will become part of the patient's medical records. All hard copy source documentation will be kept in a secure location for the time frame designated by each participating site's requirements. The electronic data will be entered and maintained on a password protected SSL website designed for this trial.

The data entered for the DEEP trial will be maintained by the DCC on a relational database. The database would be housed in a virtual environment so in the event of a hardware failure it would migrate to a new host. The data will be backed on a regular schedule with full transaction log files in use and copies of the data will be stored offsite with a secure service. In addition to the data server, the production web server will also be backed up routinely and as a virtual machine can be transitioned to different hardware automatically in case of hardware failure. All Servers are behind an enterprise firewall and access has to be granted through the firewall even within the University Network.

Database Management: A two-tiered database structure will be created. A front-end database will serve the web entry needs, using a database management system well-suited to handling updates from multiple interactive users. The data from this database will be transferred on a regular schedule to a data repository that can be used by statistical software packages. These datasets will be the basis for data queries, analyses and monitoring reports. Various versions of this database will be kept as needed, e.g. for quarterly performance reports. Access to data will be limited to those who need access to perform their tasks. The database management system is able to manage large quantities of data, to merge data from

multiple databases as required, to handle complex and possibly changing relationships, and to produce analysis datasets that can be imported into a variety of statistical analysis packages.

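### Sample size: an effect size of 0.45 with SD 21 is 9.45 VNRS points, not the stated 7.1, so the three figures cannot all be right

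*Combined protocol and SAP*

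**What the plan says.** The Sample Size paragraph (Section VI, after the Aim #4 analyses) first fixes the number of patients by a standardised effect: "To detect a minimum effect size of 0.45, a sample size of 150 subject is needed (75 per group"), under "a type I error of 0.05, a two-sided alternative hypothesis, and 80% power". It then converts this to the VNRS scale. The conversion opens with "Thus, assuming a standard deviation of 21", for which it cites a 2003 study that the reference list shows to be a trial of local anaesthetics in laceration repair (reference 10). It ends with the statement that "a difference of 7.1 can be detected between the mean VNRS scores".

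The test that the calculation should match is given under Aim #1 in the same section: "A t-test will be used to compare the mean VNRS scores between the two treatment groups". A regression adjusting for site and unbalanced baseline characteristics follows as a further comparison. The sample-size text states no baseline correlation, variance reduction or dropout allowance.

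**The concern.** For a comparison of two means, the standardised effect size is the difference divided by the SD. The plan presents 7.1 points as the consequence of 0.45 and 21, and it is not their product. At least one of the three figures is wrong.

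The 7.1 is the only statement, in units of the primary outcome, of what the trial can detect. An IRB, funder or DSMB will read it as 80% power for a 7.1-point difference. If the cited SD is correct, that is far from true, and a null result would be over-interpreted: a real 7.1-point difference would be missed almost half the time.

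The error could also reach monitoring. The Interim Analyses text makes conditional power the futility criterion ("Specifically, the conditional power will be calculated") without naming the effect to be assumed. If the DSMB uses a design effect, it has two incompatible ones to choose from.

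**Working it through.** **Inputs, all from Section VI:** effect size d = 0.45; n = 75 per arm; two-sided alpha 0.05; target power 80%; SD 21; stated difference 7.1; unadjusted t-test; interim and final boundaries ±2.96 and ±1.97 at 50% information.

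**1. The plan's effect-size claim.** Normal approximation: power = Φ(d√(n/2) − 1.960) = Φ(0.45 × √37.5 − 1.960) = Φ(0.796) = 78.7%. The noncentral t gives 78.2%. So 0.45 roughly fits 75 per arm. A full 80% would need 78 per arm (normal) or 79 (t). This shortfall is minor.

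**2. Conversion to points.**
- 0.45 × 21 = 9.45 points, not 7.1.
- 7.1 / 21 = 0.338, not 0.45.
- 7.1 / 0.45 = 15.8, the SD that would link the other two figures.

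**3. Difference detectable with 80% power at SD 21.** (1.960 + 0.842) × 21 × √(2/75) = 9.61 points. With the t distribution the effect size is 0.4605, and 0.4605 × 21 = 9.67 points.

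**4. Power for 7.1 points at SD 21.** Φ(0.338 × √37.5 − 1.960) = Φ(0.110) = 54.4%; noncentral t 53.9%. For 80% power, 138 per arm are needed (normal) or 139 (t), that is 276 or 278 in total.

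**5. If the SD were 15.8 instead.** Power at 7.1 points is 78.1% (t), and the difference detectable with 80% power is 0.4605 × 15.8 = 7.28 points.

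**6. Attempts to recover 7.1 with SD 21.**

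| Explanation tried | Result in points |
|---|---|
| Rounding of inputs: 0.445 × 20.5 to 0.455 × 21.5 | 9.1 to 9.8 |
| One-sided 0.05, 80% power | 8.53 (normal), 8.57 (t) |
| Final alpha 0.049 | 9.64 |
| 150 per arm, or paired formula with n = 75 | 6.79 |
| One-sample formula with n = 150 | 4.80 |
| Power 50%, 60%, 70% | 6.72, 7.59, 8.52 |

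None gives 7.1. Working backwards with rounding allowed, 7.1 and 0.45 need an SD between 7.05 / 0.455 = 15.5 and 7.15 / 0.445 = 16.1. Covariate adjustment would have to cut the SD from 21 to 15.78, which takes a correlation of √(1 − (15.78/21)²) = 0.66. The plan states no such correlation, and its first comparison is an unadjusted t-test.

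**7. Effect of the interim look.** With the 2.96/1.97 boundaries (normal approximation), power is 78.5% at 0.45 and 54.2% at 0.338. The like-for-like fixed-design values are 78.7% and 54.4%, so the interim analysis costs almost nothing and does not explain the gap.

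**8. Illustration for futility.** Suppose the interim z is 0.25 at half information and a design effect is assumed. The expected final z (drift) is d√37.5: 2.756 for 9.45 points and 2.070 for 7.1 points at SD 21. Conditional power is 1 − Φ[(1.97 − 0.25√0.5 − 0.5 × drift)/√0.5], which is about 28% under 9.45 points and 14% under 7.1. These fall on opposite sides of the plan's example threshold of 20%.

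**The case against.** The best defence is that the number of patients does not depend on 7.1. The plan ties 150 to the standardised effect of 0.45, and SD 21 and 7.1 come afterwards as a translation into points. If either of those two is the wrong entry, the sample size, test, alpha and boundaries all stand. The plan nowhere calls 7.1 a clinically important difference or uses it in a decision rule, and the Outcomes section describes the trial as a pilot. On this view the 54% figure belongs to the scenario that the text supports least.

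Much of this is fair. No design failure has been shown, and 54% counts as a shortfall only if 7.1 points at SD 21 was the target. It is also fair that the documents cannot settle which figure is wrong. The fit with 75 per arm supports 0.45, but says nothing about 21 against 15.8, and a citation does not show that 21 was copied correctly. Finally, the futility illustration applies only if the DSMB assumes a design effect, which the plan does not say.

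What does not stand is the idea that the figure can be left alone. It is wrong as written, it is the only one in outcome units, and a reader cannot tell which of the readings applies.

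**Conclusion.** The point holds. The figures 0.45, 21 and 7.1 are mutually inconsistent, and no rounding, sidedness, power level or interim adjustment tried here reconciles them.

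The size depends on which entry is wrong. For a two-sided t-test at 0.05 with 75 per arm and complete data:
- **SD 21 correct:** power is about 54% at 7.1 points and 78% at 9.45, and about 9.7 points is detectable with 80% power. The stated 7.1 understates the detectable difference by about 2.6 points (9.67 − 7.1).
- **SD about 15.8 correct:** 7.1 is close to right (78% power; 7.3 points for 80%), and the printed SD is the error.

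Keeping 0.45 and 21 is the natural reading, because 0.45 roughly matches the sample size and 21 is the figure with a source. Only the sponsor can confirm it. This is a wrong figure in the justification of the primary analysis and must be corrected. It does not by itself show that the trial is too small.

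**What to change.** State which of the three entries is wrong and correct the paragraph accordingly.

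1. **If 0.45 and SD 21 stand:** delete 7.1 and write, for example:

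> With 75 per group, an SD of 21 and a two-sided type I error of 0.05, the trial has about 78% power for a 9.45-point difference (effect size 0.45); the difference detectable with 80% power is about 9.7 points.

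2. **If SD 21 is the wrong entry:** state and justify the SD of about 15.8 that yields 7.1.

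3. **If 7.1 points at SD 21 was the intended target:** say that 150 patients give about 54% power for it, and that 80% would need 139 per arm (278 in total).

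Under 1 or 2, amend the preceding sentence in the same edit so that it gives about 78% or approximately 80% power for 0.45. Otherwise the paragraph would carry two powers for one effect. If the DSMB's conditional power is to use a design effect, name the reconciled value in the monitoring plan.

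Options 1 and 2 cost only protocol and SAP wording, with no extra patients. Option 1 makes the stated detectable difference less favourable. Option 3 obliges the plan to disclose low power for its own target.
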